The goal of the third phase of FFT certification process is to move into a partnering relationship between the provider and FFT-LLC to assure on-going model fidelity, as well as impacting issues of staff development, interagency linking, and program expansion.

For this efficacy study, the control condition will be the usual services that would available for the YP and their family delivered to YP in child social care and related agencies. Prior to recruitment and randomisation a potential SAU intervention will be identified and selected by the caseholding practitioner in a consultation with the FFT-G supervisor/supervisor-in-training. The nature of the intervention will vary depending on availability in each site and the particular needs of the YP but there will be existing services in the local authority that are available for cases with contextual risk. This will be decided by caseholders prior to randomisation to ensure that an SAU intervention is available directly after randomization. All YP and Primary Caregivers (PCG) will be reimbursed for each assessment with a £30 shopping voucher. The intervention will be delivered to RCT participants between June 2024 and March 2026, with 6 month boosters provided to some families between April and September 2026. Booster sessions are follow-up sessions intended to consolidate the family's learning and knowledge especially to help resolve or overcome setbacks and new challenges. A caseholder or family member can request boosters directly from the FFT-G service.

Figure 1: FFT-G logic model

Impact evaluation

Research questions or study objectives

1. What is the difference in the volume (or variety) of self-reported delinquency between YP randomised to receive FFT-G and those randomised to receive SAU?
2. What is the difference in secondary outcomes between YP randomised to receive FFT-G and those randomised to receive SAU?
3. ~~What mediates~~ Do any proposed mediators mediate the relationship between intervention arm and self-reported delinquency? Potential mediators include parental supervision and monitoring, family functioning, parental and YP self-efficacy and YP attachment representations.
4. ~~What moderates~~ Do any proposed moderators moderate the effect of treatment and are there subgroup differences? Specific moderators include callous-unemotional traits, temperamental irritability, presence of offending behaviours at baseline.

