Delivery team: The FPM senior management team consists of [name] (Project Director/FPM CEO) who will oversee the implementation and clinical quality assurance and [name] (FFT-G Programme Manager) who will be the main contact person for the project. [name] (FPM CEO/Business Director) will provide back-up support, implementation advice and monitoring feedback reports. FPM Data Analyst, [name], will be involved throughout the project, especially during the mobilisation period to ensure the development of efficient data systems (e.g. study consultation tracker, case management spreadsheets, joined research and provider tracker), which proved indispensable for the successful delivery of the pilot RCT.

Each Borough will have a designated FFT-G team consisting of one clinical supervisor/supervisor-in-training and two therapists with dedicated admin support. In this

first year the supervisor in training will act as the operational manager of the team and will provide case management oversight of therapist activities and promote adherence to the model whilst holding their own (reduced) caseload of two families. They will also be responsible for identifying eligible cases through data retrieval and review processes and in offering consultations to allocated workers. They will be trained in this process and supported by the Programme Manager.

In addition, we will include a floating/peripatetic FFT-G therapist who can work across all three Boroughs to (a) ensure sufficient coverage in cases of therapist illness/maternity leave/annual leave/turnover; (b) manage capacity in demand. This will need to be a therapist with some prior FFT experience. We consider that this post will provide assurance against workflow fluctuations and also as a mitigation against staff sickness and turnover.

In the second year, supervisors will then also be doing the weekly supervision of the clinical work with training of the supervisor provided by FFT-LLC as we move the second stage of the FFT licence.

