[name] will have oversight of overall and day to day trial management, of trial setup, of trial protocols, obtaining ethical approval, analysis and write-up, and management of the project Research Fellow. Profs [name] and [name] will both contribute to trial setup, management, analysis and write-up and discussion and negotiation with stakeholders. They will have a key role in the development of the assessment battery and primary outcome measure. [name] will also contribute to staff recruitment and management. The research fellow will be responsible for day-to-day management of the trial and will also conduct recruitment and assessment activities. Research assistants will conduct the majority of recruitment and assessment activity as well as data entry and cleaning. Employment of research assistants will be on a staggered basis to align to recruitment and assessment activities.

Randomisation (but not data management) will be conducted by King's College Clinical Trials Unit.

LA stakeholders: The project partners are three London Local Authorities: Tower Hamlets, Haringey and Redbridge. We already have established contact and they have each appointed a designated lead in their Local Authority who will be the main point of contact between FPM and the Local Authority. These leads will be instrumental in forming and chairing a local steering group in each Authority which will meet monthly and will ensure operational issues are addressed in a timely fashion during the project.

Advisory Group: We are planning the establishment of an Advisory Board consisting of members from FPM, the University of Greenwich, representatives from each participating Local Authority and other external members with specific knowledge to advise the group. This is likely to be held on a quarterly basis to offer cross-Borough opportunities for problem-solving and to unite the different stakeholders to this RCT project.

No conflicting interests.

Risks

Please Appendix C: Risk Register.

Timeline

Dates	Activity	Staff responsible/ leading
July-Dec 2023	Mobilisation	FPM
February-March 2024	Protocol finalised following ethics review	UoG
January – June 2024	FFT-G training phase	FPM/FFT LLC
May-June 2024	Statistical analysis plan and protocol published on ISRCTN	UoG
May 2024	RCT referrals start	FPM
June 2024 – September 2025	Randomisation and baseline data collection	UoG/CTU
July 2024 - March 2026	Delivery of intervention	FPM
December 2024 – March 2026	Post-treatment data collection	UoG

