calculate effect sizes for primary and secondary outcomes. We will use structural equation modelling to test for mediators of treatment (which are listed as secondary outcomes above).

Based on evidence from the pilot trial it is possible that some outcome variables may be skewed, in particular the primary outcome. We will determine whether transformation or scaling is appropriate depending on the skew and distribution of the data.

The analytical approach has been determined a priori and will be conducted with R Studio and SPSS.

Primary outcome analysis

The primary outcome is the ISRD4 total score which is a continuous variable. All YP will complete this measure at baseline, 6 months after randomisation and 12 months after randomisation. The main test of treatment effect will be at 12 months after randomisation. The total score uses a sum of the total volume of delinquent acts using 14 questions. The response scale for each question can be from 0 to whatever the total number of acts reported is (although see above for transformation approach). A hierarchical linear mixed model will be used with site as a fixed effect.

Regression models will be adjusted by the baseline number of offences in the six months prior to randomisation and stratification factors; age group and site, as covariates. The regression model specification is detailed in eq. 1.

Eq. 1

OFF6i,j = α + β 1 (allocation)i,j + β 2 (OFF0)i,j + β 3 (age)i,j + β 4 (site)j + β 4 (study)j ϵ

Secondary outcome analysis

The secondary outcomes are:

- YP Child Criminal Exploitation measured by items added to the Self-Report Delinquency Scale (YP report).
- YP Substance Misuse measured by ISRD3 substance misuse subscale (YP report).
- YP Conduct Problems measured by the conduct problems subscale of the SDQ (YP and parent report).
- YP mental health and adjustment measured by total score and impact score on the SDQ (YP and parent report; impact score parent report only).
- Parental mental health measured by the DASS-21 (parent report).

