We will add three additional questions to the SRDS scale asking about missing from home episodes, storing or transporting drugs or weapons and engaging in sexual activity in exchange for money or goods. For each of these additional questions and for each of the 14 SRDS questions we will ask whether anyone has tried to involve the YP in these behaviours, who they were and how many times this happened. The CCE scale will be calculated from the total volume of how many times they were involved by others in these 17 behaviours and will range from 0 to the total number reported (although see above for transformation approach).

The ISRD3 substance misuse scale asks about the use of 5 substances, with response options varying depending on the substance. The scale can be from 0 to whatever the total number of times substances were used is (although see above for transformation approach). In addition, we will add questions on use of synthetic substances and on non-prescribed medications. We will calculate an additional total scale with these additional items and this will be analysed separately from the main ISRD3 substance misuse subscale.

SDQ subscales, including the conduct problems subscale, contain 5 items scored 0, 1 and 2, with scale values from 0 to 10. The SDQ total difficulties scale ranges does not include the prosocial scale and therefore ranges from 0 to 40. The impact score is computed by summing questions on distress and impairment and ranges from 0 to 10.

The DASS-21 contains 21 items, 8 for each of the anxiety, depression and stress subscales, with response values of 0, 1, 2 and 3. We will calculate the total score which ranges from 0 to 63.

All secondary outcome scores are treated as continuous, and a hierarchical linear mixed model will be used with site as a fixed effect. As noted above, we will determine whether transformation is appropriate depending on the data.

Subgroup analyses

Any subgroup analyses will be exploratory in nature. Sample size calculations for the trial have been conducted on the basis of the main primary outcome analysis, not for subgroup analyses. Therefore, it is possible that subgroup analyses may be underpowered. We will conduct post-hoc power analyses when all data has been collected and frame our reporting of these analyses accordingly. Analyses will be conducted using interaction terms.

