The subgroup analyses proposed in the protocol were differences in gender, age, temperamental irritability, CU traits and presence of offending behaviour at baseline as identified by caseworker.

We aim to conduct the following analyses

- Race: we will explore whether FFT was equally effective with YP and parents from
 minoritised backgrounds as for those from White backgrounds. Specifically, we would
 expect to compare those of Black backgrounds to those of White backgrounds and
 compare those of South Asian backgrounds to those of White backgrounds. This is on
 the basis that those from minoritised backgrounds may face more structural
 challenges that may impede the impact of FFT-G.
- Age: we will explore whether age moderates the effect of FFT using a continuous measure of age. We may expect that FFT-G may work better for those who are younger and therefore at an earlier age of their criminal careers.
- Gender: we will explore whether FFT is as effective with YP who identify as female as much as with those who identify as male. We are unlikely to have an adequate sample size to include those who do not identify as male or female in these analyses so will use a dichotomous measure of gender. As FFT-G has been predominantly developed, delivered and evaluated with males we may expect less impact on females.
- Callous-Unemotional (CU) Traits: we will explore whether the presence of CU traits moderates the effect of treatment. Specifically, we would hypothesise that YP with elevated CU traits would be less responsive to treatment. CU traits will be measured with the CU Traits MAP, consisting of 4 items with a total scale of 0 to 12.
- Temperamental Irritability: we will explore whether the presence of temperamental irritability moderates the effect of treatment. Specifically, we would hypothesise that YP with elevated irritability would be more responsive to treatment. Temperamental irritability will be measured with 3 items from the SDQ and ODD subtyping items, with a total scale of 0 to 9.
- Offending at baseline: we will explore whether FFT reduces self-reported delinquency more in YP whose referring practitioner reported that they were offending at baseline compared to those who reported to not be offending at baseline. This will use a dichotomous score.

Further analyses

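### The race subgroup contrasts can be confounded with borough differences in FFT-G team and SAU, because site enters the model only as a main effect

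*SAP*

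**What the plan says.** **The race analysis.** SAP, Subgroup analyses (Race): the evaluators "expect to compare those of Black backgrounds to those of White backgrounds", with a matching South Asian versus White comparison. The stated reason is that structural challenges could weaken FFT-G's impact for minoritised families. On method the section says only: "Analyses will be conducted using interaction terms". On status it says: "Any subgroup analyses will be exploratory in nature". It adds that these analyses may be underpowered.

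**Site in the model.** SAP, Primary outcome analysis: "A hierarchical linear mixed model will be used with site as a fixed effect". Eq. 1 lists allocation, baseline offending, age, site and study, with no product of allocation and site. The secondary outcome section repeats site as a fixed effect. The subgroup model is not written out, and neither document mentions an arm-by-site term.

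**Delivery.** Protocol, Stakeholders and interests: "Each Borough will have a designated FFT-G team", made up of one supervisor or supervisor-in-training and two therapists. The sites are "Tower Hamlets, Haringey and Redbridge". There is also a "floating/peripatetic FFT-G therapist who can work across all three Boroughs". Footnote 7 notes that two sites are new and that all the teams are new.

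**Comparator.** Protocol, Intervention, on SAU: "The nature of the intervention will vary depending on availability in each site". The same sentence adds that it also depends on the young person's needs.

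**The concern.** Both halves of the treatment contrast can differ by borough: the team that delivers FFT-G and the services it is compared with. A site main effect absorbs differences between boroughs in the level of offending. It does not absorb differences in the effect of treatment. If one ethnic group is concentrated in a borough where FFT-G adds less, or where SAU is stronger, the arm-by-ethnicity coefficient carries part of that borough difference even when ethnicity plays no role.

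A statement that a family therapy works less well, or better, for Black or South Asian families is consequential. The SAP also gives a direction and a cause in advance, so a gap in that direction could be taken as confirmation. As planned, a reader could not check: SAP, Imbalance at baseline, tabulates characteristics by arm only, and no ethnicity-by-site table or site-specific effect is planned.

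**Working it through.** The documents give no figure for the race tests, so there is none to reproduce.

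**Inputs from the documents.** Three sites; 1:1 allocation stratified by site; 288 randomised with up to 10% loss at each of two follow-ups, so 288 × 0.9 × 0.9 = 233 analysed; baseline-outcome correlation 0.523; pilot effect 0.36 SD, used as the scale for a team effect.

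**Assumptions.** Equal site sizes, normal outcome with SD 1, two-sided 5% tests, no true ethnic difference in effect. Ethnic mix and site effects are varied over a range.

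**Step 1, formula.** Allocation is balanced within site, so site main effects do not alter the arm-by-ethnicity coefficient in expectation. The coefficient estimates the difference between groups in average site effect. With benefit d_s in site s, and p_s the minority share of the two compared groups:

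gap = Σd_s(1−p_s)/Σ(1−p_s) − Σd_s p_s/Σp_s

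**Step 2, two groups.** Here Σp_s = Σ(1−p_s) = 1.5 throughout. Rejection rates and RMSE come from simulations with an assumed 156 participants in the two compared groups (156/233 = 67%). Rejection ranges span separate runs.

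| Benefit by site | Minority share | Gap (SD) | Rejection, planned model | RMSE, planned / with arm-by-site |
|---|---|---|---|---|
| 0.2/0.3/0.4 | 60/50/40% | 0.47/1.5 − 0.43/1.5 = 0.027 | – | – |
| 0.1/0.3/0.5 | 70/50/30% | 0.53/1.5 − 0.37/1.5 = 0.107 | 6.5–6.6% | 0.343 / 0.346 |
| 0.1/0.3/0.5 | 80/50/20% | 0.57/1.5 − 0.33/1.5 = 0.160 | 8.4–9.0% | 0.366 / 0.379 |
| 0/0.3/0.6 | 80/50/20% | 0.63/1.5 − 0.27/1.5 = 0.240 | 10.3–11.8% | 0.398 / 0.369 |

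Simulated gaps agree with the formula (0.10–0.11, 0.16–0.17 and 0.24–0.25 in the last three rows). With arm-by-site added, bias is at most 0.014 SD and rejection 4.7–5.8%. The standard error rises from about 0.325 to 0.330–0.377, that is 2 to 16%.

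**Step 3, both contrasts together.** A second simulation had 3 × 78 = 234 analysed, baseline adjustment, four ethnic groups and 3,000 runs. One borough has no effect and the other two have Δ = 0.36 SD. The formula then reduces to gap = Δ × (share of the minority group living in the weak borough − same share for the White group). A positive value means less benefit for the minority group.

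- Same mix everywhere: 0; rejection 5%.
- Moderate (Black 45% of the weak borough, 20% elsewhere): Black–White 0.36 × (0.45/0.85 − 0.35/0.90) = +0.05, rejection 5.9%. South Asian–White 0.36 × (0.10/0.95 − 0.35/0.90) = −0.10, rejection 6.6%.
- Strong (Black 55% against 10–15%): Black–White 0.36 × (0.55/0.80 − 0.30/0.75) = +0.10 (simulated +0.11), rejection 6.9%.
- Extreme (one group 80% of each borough): Black–White 0.36 × (0.80/0.90 − 0.10/1.00) = +0.28 (simulated +0.29), rejection 17%.

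With Δ = 0.54 the simulated Black–White gaps are +0.07, +0.17 and +0.44, with rejection of 6.5%, 8.3% and 33%. In every scenario arm-by-site brings the bias to within 0.007 SD of zero and rejection to 4.7–5.6%.

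**Step 4, direction.** Keep the moderate mix and Δ = 0.36 but move the weak team to another borough. Black–White becomes 0.36 × (0.20/0.85 − 0.25/0.90) = −0.02, and South Asian–White becomes 0.36 × (0.45/0.95 − 0.25/0.90) = +0.07. Both signs reverse.

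**Step 5, precision.** In Step 3 the Black–White standard error under the planned model is 0.283 to 0.316, so 80% power needs roughly 2.8 × 0.283 = 0.79 to 2.8 × 0.316 = 0.88 SD. Adding arm-by-site moves it from 0.297 to 0.300 (moderate), 0.316 to 0.328 (strong) and 0.283 to 0.449 (extreme, +59%).

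**The case against.** **The bias needs two conditions that the documents do not establish.** Ethnic mix and treatment effect must both differ by borough, and in related patterns. A reader might infer that a weak team will show up as FFT-G working less well for that borough's main ethnic group. The documents do not support that: they give no ethnic mix and no site effects, the bias can run either way, and it can fall on the other contrast. This stands, and the claim is limited to what can happen.

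**Delivery is partly shared.** There is a floating therapist, one programme manager, common training and adherence monitoring; fidelity is reported; and the process evaluation examines locality factors and experience by ethnic background. SAU also depends on individual need. These may narrow team differences or help a weak team to be noticed. None of them enters the race estimate.

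**The SAP calls the analyses exploratory.** That label and the planned post-hoc power analyses address precision. They do not address bias.

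**The overall difference may be the quantity wanted.** If minoritised families are served by weaker local provision, the unadjusted contrast describes that. This is a fair reason to keep the planned model. It is also a reason not to read its result as an effect of ethnicity without the within-site contrast.

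**Adjustment costs precision.** In the two milder simulated rows of Step 2 the planned model has slightly the lower RMSE; in the third it has the higher. Under extreme segregation with Δ = 0.36, the planned model's RMSE is √(0.29² + 0.283²) = 0.41 against 0.449; with Δ = 0.54 it is √(0.435² + 0.284²) = 0.52 against 0.449. Neither model dominates, so replacing the planned model is not justified.

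**Conclusion.** The concern holds as a possibility that the plan gives no means of detecting. With site as a main effect only, borough differences in FFT-G team or SAU can load onto the race interaction, in either direction. That site has no further role is inferred from Eq. 1 and from the absence of any other term, since the subgroup model is not written out.

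Under assumed strong differences the false gap is about 0.1 to 0.25 SD with 6 to 12% false positives. It exceeds that only under extreme segregation. Under mild differences it is about 0.03 SD or less, and with equal ethnic mix it is zero. In most scenarios the bias is smaller than the contrast's own standard error of about 0.3 SD, so the main risk is misreading an estimate rather than a frequent false significant result.

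A reader might also infer that every moderator model needs arm-by-site terms. The calculations cover ethnicity only, and nothing in the documents ties age, gender, CU traits, irritability or baseline offending to borough. That extension is not supported.

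**What to change.** In SAP, Subgroup analyses (Race), add text to this effect:

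> Each race contrast will be reported from the planned model and, beside it, from a model that adds arm-by-site terms. A race difference that is not seen within site will not be attributed to ethnicity. Ethnicity will be tabulated by site and arm.

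Whether a difference is seen within site should be judged on the estimate and its interval. Loss of significance alone is a poor guide, because the within-site standard error is larger.

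**Cost.** A few sentences, one extra model per race contrast (two further degrees of freedom with three sites) and one table. Ethnicity and site are already recorded, and the primary analysis is unchanged. The within-site contrast is less precise: about 2 to 16% in the two-group scenarios, and up to about 59% if boroughs are extremely segregated. In that last case the wide interval shows how little the trial can say about ethnicity separately from borough.

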		Attachment representation measured by YP report: AAQ (Bodfield et al., 2020)	

YP self-efficacy measured by YP report: NGSE (Chen et al., 2001)

CU traits measured by YP and parent report: CU Traits MAP (Hawes et al., 2020)

Temperamental irritability measured by YP report: ODD subtyping DSM items (Stringaris & Goodman, 2009)

YP School attendance and truancy measured by parent report; and YP report from ISRD4

Age; gender; ethnicity; SES; household composition; parent relationship to YP measured by parent and/or YP report

Service being seen; days from first caseworker contact to randomisation measured by administrative data

Sample size calculations overview

Sample size calculations are not determined on the basis of a priori MDES but rather results from the pilot RCT.

		Protocol	Randomisation
Pilot study Effect Size		g = 0.36 [-0.32,1.03]	
Pre-test/ post- test correlations	level 1 (participant)	0.523	
Alpha ⁶		0.05	
Power		0.8	
One-sided or two-sided?		One sided	

⁶ Please adjust as necessary for trials with multiple primary outcomes, 3-arm trials, etc., when a Bonferroni correction is used to account for family-wise errors.

9

			Protocol	Randomisation
Number of participants		Intervention	144	
	of	Control	144	
	Total	288		

Sample size estimates for a full efficacy RCT were calculated using clincalc.com and checked against G^* Power calculations. Estimates used 80% power and p = 0.05 with an enrolment ratio of 1. Power calculations used one-sided tests because there is no recorded case of FFT having iatrogenic effects.

The primary outcome in the efficacy study is *Offending*: Self-reported delinquency (SRD) - International Self-Report Delinquency Study 4 survey offending scale (ISRD4; Marshall et al., 2022). This was not the primary outcome in the pilot study. Whilst a number of trials of FFT have been conducted with offending as a primary outcome, and a previous trial of FFT-G did include delinquency as a primary outcome, it recruited court mandated youth who were offending. The focus of the pilot was instead YP at risk of criminal exploitation recruited from social care.

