Therefore, the anticipated primary outcome in the pilot study was CCE as recorded on agency systems. During the pilot study, it became clear that this was not recorded reliably and so two co-primary outcomes collected directly from participants were used instead: PCG reported family functioning (total scale score) and YP reported conduct problems (CP; subscore of the SDQ). As a result, power calculations for this efficacy trial did not make use of SRD data from the pilot study. Based on the effect size for PCG-reported Family Functioning outcome in the pilot study (g = 0.36 (-0.32,1.03)), clincalc.com returned 238 participants, increased to 288 to account for up to 10% loss to follow-up at each assessment time point. Based on the effect size for YP-reported CP (g = 1.15 (0.13,1.52)), clincalc.com returned 42 participants, increased to 51 to account for 10% loss to follow-up at each assessment time point. After discussion with the YEF Assistant Director of Evaluation, the decision was taken to use the upper end of this sample size calculation range (N=288). Any harmful effects will be monitored through serious incident reporting. The pre-test/post-test correlation also mirrors the results of the pilot trial (i.e., 0.523).

However, as subsequently requested by the YEF, this trial will use self-reported delinquency as the primary outcome. The rationale for this is:

- A core YEF strategic aim is to understand what works to reduce crime and violence, so YEF aims to select offending as the primary outcome in all YEF studies where it is plausible that the intervention will reduce it, e.g. it is included in the theory of change
- The primary outcome must be measured using a valid and reliable measure and there were no valid and reliable measures of other relevant outcomes that are highly connected to crime e.g. child criminal exploitation.
- The mitigations included since the pilot study to increase the chance of seeing impact on offending (e.g. screening YP, introducing anonymous reporting of outcomes by YP)
- The co-primary outcomes from the pilot study will be included as secondary outcomes so that it will still be possible to test for intervention effects on these.

Participants

Participants will be YP between 10-17 at risk of CLDN involvement or CCE being seen by child social care or related agencies in three London local authorities and their primary caregiver (PCG).

Inclusion criteria - YP and families

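### The baseline-offending moderator test is a linear-model interaction on an act count, with no robust standard errors and no stated scale, so its error rate can be wrong and its result can be misread

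*SAP*

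**What the plan says.** SAP, Primary outcome analysis: the outcome is the total number of acts over 14 ISRD4 items, each with no upper limit. It is called continuous. "A hierarchical linear mixed model will be used with site as a fixed effect". SAP, Analysis: skew is expected, above all in the primary outcome, and the choice of transformation waits until the data are seen.

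SAP, Subgroup analyses: "Analyses will be conducted using interaction terms". For offending at baseline, "we will explore whether FFT reduces self-reported delinquency more in YP whose referring practitioner reported that they were offending at baseline", scored yes/no. For age, "we will explore whether age moderates the effect of FFT", with age continuous and larger effects expected in younger YP. All subgroup analyses are labelled exploratory and possibly underpowered.

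Protocol, Consultation: the baseline flag is the referring practitioner's belief, recorded before randomisation. Protocol, Method of collection for offending and CCE data: the pilot delinquency measure (a different scale) was strongly skewed and few respondents admitted offences.

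Neither document names a count model, robust standard errors, or the scale (difference in acts, or ratio) on which moderation is judged.

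**The concern.** The moderator is meant to separate YP who offend from those who do not. If it succeeds, the two groups differ in mean count and, for skewed counts, in variance. Two separate problems follow.

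1. **Size.** The ordinary interaction test assumes one residual variance. If the high-variance group is the smaller one, the standard error is too small; if it is the larger one, too big.
2. **Scale.** A linear interaction compares absolute falls in acts. A group with few acts cannot fall by many, so the same percentage reduction in both groups appears as a larger effect in the flagged group.

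Baseline offending is named in the protocol's research question 4. The protocol's background also reports that the earlier FFT-G trial found benefit in high-risk but not low-risk youth, so a spurious interaction here could look like replication.

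**Working it through.** **Inputs from the documents.** There is no stated error rate or power for a subgroup test to reproduce. The planned sample is 238 before attrition, and 238 × 1.1 × 1.1 = 287.98, i.e. 288. Losing 10% at each of two time points leaves 288 × 0.9 × 0.9 = 233.3, so 233-234 are taken as analysed. Allocation is 1:1. The interaction test is taken as two-sided at 5%, because the SAP gives no sidedness for it.

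**Inputs assumed.** The documents give no subgroup means, share flagged or dispersion. Ranges used: flagged v unflagged means from 5 v 3 to 8 v 1.5 acts, with 6 v 2 and 8 v 1 as further cases; 20% to 70% flagged; gamma-Poisson counts, with variance m + k·m² and k = 1.5 or 2.

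**Size, by formula.** Let p be the share flagged and v1, v0 the variances in flagged and unflagged YP. With 1:1 arms:

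- true variance of the interaction = (4/N)·[v1/p + v0/(1-p)]
- variance the pooled test assumes = (4/N)·[p·v1 + (1-p)·v0] / [p(1-p)]
- R = true/assumed = [(1-p)·v1 + p·v0] / [p·v1 + (1-p)·v0]
- true size = 2·[1 - Φ(1.96/√R)]

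With k = 1.5:

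- Means 8 v 1.5: v1 = 8 + 1.5×64 = 104; v0 = 1.5 + 1.5×2.25 = 4.875. At p = 0.2, R = (0.8×104 + 0.2×4.875)/(0.2×104 + 0.8×4.875) = 84.175/24.7 = 3.41, so the size is 28.8%.
- Means 5 v 3: v1 = 5 + 1.5×25 = 42.5; v0 = 3 + 1.5×9 = 16.5. At p = 0.2, R = (34 + 3.3)/(8.5 + 13.2) = 37.3/21.7 = 1.72, so the size is 13.5%.

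At p = 0.5, or when v1 = v0, R = 1 and the size is 5%.

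**Size, formula and simulation.** Rejection with no effect in anyone, ordinary standard errors:

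| Flagged v unflagged means; method | 20% flagged | 30% | 50% | 70% |
|---|---|---|---|---|
| 5 v 3; formula | 13.5% | 10.1% | 5.0% | 1.9% |
| 5 v 3; simulation, no covariates | 12-13% | 9-11% | 5% | 2% |
| 8 v 1.5; formula | 28.8% | 18.1% | 5.0% | 0.4% |
| 8 v 1.5; simulation, no covariates | 30-32% | 19% | 5-6% | 0.4-0.5% |
| 6 v 2; baseline, site, age adjusted (k = 2) | 22.0% | 17.2% | 4.5% | 1.2% |
| 8 v 1; baseline, site, age adjusted (k = 2) | 32.8% | 20.6% | 4.1% | 0.5% |
| 8 v 1.5; random-intercept model, 12 months v baseline | 28% | 19% | 6% | 0.6% |

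The pattern is therefore not peculiar to an unadjusted analysis or to a single-time-point one. In the adjusted simulations:

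- equal means in the two groups give 4.3%
- HC3 robust errors give 3.1-4.4%
- log(1+x) on outcome and baseline gives 2.3-12.1%

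**Scale.** With a 40% reduction in both groups, the interaction in acts is -0.4×8 + 0.4×1.5 = -2.6 for means 8 v 1.5, and -0.4×5 + 0.4×3 = -0.8 for 5 v 3. The ratio of rate ratios is 0.6/0.6 = 1 in both cases.

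- Ordinary linear test, 8 v 1.5: significant in 33-52% of trials at 20-50% flagged and 12% at 70%.
- Ordinary linear test, 5 v 3: significant in 4-16%.
- These figures mix the two problems. With HC3 errors, which isolate scale, the 8 v 1.5 case gives about 14-37% at 20-50% flagged.
- log(1+x) does not remove it: at a rate ratio of 0.5 in both groups (means 6 v 2 and 8 v 1), 8.1-36.1% are significant.
- A log-link Poisson model with HC3 errors rejects in 4.2-7.0% at common rate ratios of 1.0, 0.7 and 0.5.

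**Age.** Assuming mean acts rise from 1 or 2 at age 10 to 6 at age 17, null rejection is 6.4-8.5%. A common rate ratio of 0.7 gives 10.8-18.3% significant, and 0.5 gives 22.9-37.3%. The larger absolute fall is then in older YP, against the direction the SAP expects. The log-link model gives 4.1-6.5%.

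**The case against.** The best defence has five parts.

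- **The tests are exploratory, and the SAP promises to frame their reporting accordingly.** That covers low power. It does not cover false positives at several times the nominal rate, which the SAP does not mention.
- **Transformation is left open.** True, but it is undecided and data-driven, it changes what the interaction measures, and log(1+x) is only a partial cure.
- **The flag may separate self-reported counts weakly.** It is a practitioner's belief, the outcome is YP self-report, and the protocol says 80% of pilot YP reported little or no offending. This stands as a reason to take the milder end of the range seriously. At 5 v 3 the null rejection at 20% flagged is still 12-13%.
- **A larger absolute fall in acts is a fair reading of reducing delinquency more.** This stands. The gap is that the SAP does not say which scale answers the question.
- **A better main model would remove the problem.** This stands if the main model becomes a log-link count model with robust errors and the interactions are fitted in it. It does not stand if the repair is a transformation, or robust errors alone, which leave the scale open.

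A reader might infer that the error rate is always wrong, or that an equal proportional effect will always be declared moderation. The documents do not support either: size is correct near a 50:50 split or with equal variances, and the second is a probability that can be as low as about 5%. Nor do they support treating age as an equal problem, because they give no age gradient in offending.

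**Conclusion.** The point holds in conditional form. With ordinary standard errors, the baseline-offending interaction test can have the wrong size if flagged YP have a higher mean and variance. Over assumed means from 5 v 3 to 8 v 1.5 acts, null rejection is about 12-32% at 20% flagged, 9-21% at 30%, about 5% at 50% and 0.4-2% at 70%. Separately, with no scale stated, an equal 40% reduction gives a significant absolute interaction in about 5-50% of trials, depending on means and split, and this may be misread as differential response. For age, size inflation is minor and the scale issue needs an undocumented age gradient.

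All magnitudes rest on assumed means, split and dispersion. What the documents do establish is that the SAP sets neither a robust variance nor a scale. This is worth correcting before analysis; it does not affect the main treatment comparison.

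**What to change.** In the SAP, Subgroup analyses:

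1. Require heteroscedasticity-robust standard errors for every interaction test on the ISRD4, CCE and substance-use counts.
2. State in advance the scale on which moderation is judged, and test the ratio of rate ratios in a log-link count model with robust errors.
3. Report subgroup effects with confidence intervals on both the ratio and the absolute scale.
4. If the main model is changed to a log-link count model with robust errors, carry it through to the subgroup interactions.

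The cost is SAP wording, a few lines of code and a sentence explaining ratio-scale results. The robust count-model test can be slightly liberal (about 4-7% at nominal 5%). Conduct and data collection do not change.
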